5. STUDY POPULATION

5.1. Number of Patients

A suitable number of potential patients will be screened in order that approximately 55 patients successfully meet the inclusion and exclusion criteria and continue into the Treatment Phase. Approximately thirty patients are expected to be enrolled in Cohort 1, approximately 10 in Cohort 2 and approximately 15 in Cohort 3. The sample size is not based upon statistical powering, but the number is considered as sufficient to initially explore the endpoints and their relationship with SMT C1100 plasma exposure.

Patients who withdraw or who are withdrawn during the Treatment Phase may be replaced if the study has not yet reached full enrolment at the time of withdrawal. Patients who withdraw or who are withdrawn for an AE considered related to SMT C1100 will not be replaced.

Efforts will be made, in Cohorts 1 and 2, to balance the study populations and attempt to have at least 50% of the boys with a fat:water fraction greater than or equal to 0.15. Efforts will also be made such that half of the boys are greater than or equal to 8 years of age at screening. Such attempts will be made manually rather than via an automatic system; achieving these recruitment goals will be attempted but complete balance will not be enforced.

All patients in Cohorts 1–3, will be eligible to be rolled into the Extension Phase.

Study Number: SMT C11005 Protocol	Compound No.: SMT C1100 Version: 5.0 24Feb2017
---	---

5.2. Eligibility Criteria

5.2.1. Main Study

5.2.1.1. Inclusion Criteria

To be enrolled patients must meet all selected criteria for their cohort:

Criterion Number	Criterion	Cohort 1	Cohort 2	Cohort 3
1	Be able to provide written informed consent/assent as per local requirements.	✓	✓	✓
2	Be male	✓	✓	✓
3	Be aged ≥ 5 years to <10 years of age (from 5 th birthday to 10 th birthday)	✓	✓	NA
4	Have phenotypic evidence of dystrophinopathy based on the onset of characteristic clinical symptoms or signs (e.g., proximal muscle weakness, waddling gait, and Gowers' manoeuvre), an elevated serum creatinine kinase level, and ongoing difficulty with walking	✓	✓	✓
5	Have prior confirmation of the DMD diagnosis through: Documentation of the presence of a mutation in the dystrophin gene as determined by gene sequencing from a laboratory certified by the College of American Pathologists, the Clinical Laboratory Improvement Act/Amendment or an equivalent organisation. Or Documentation of the absence of dystrophin in the muscle (via biopsy)	✓	✓	✓
6	Be willing and able to comply with two muscle biopsy procedures	✓	✓	NA
7	Be able to undergo MRI examination	✓	✓	✓
8	Patients must have used stable systemic corticosteroids (prednisone, prednisolone or deflazacort) for a minimum of 6 months immediately prior to the start of the Treatment Phase, with no significant change in dosage or dosing regimen (not related to body weight change) and a reasonable expectation that dosage and dosing regimen will not change significantly for the duration of the study	✓	✓	✓
9	Have the ability to walk at least 300 meters unassisted during the screening 6MWD and be below the protocol-specified threshold for 80%-predicted 6MWD	✓	✓	NA
10	Have results of two 6MWD by Baseline determined as valid. The results of the second 6MWD (baseline) must be within 20% of the first 6MWD (screening)	✓	✓	NA
11	Have cardiac ECHO measurements showing an ejection fraction of $\geq 55\%$ and fractional shortening of $\geq 28\%$	✓	✓	NA
12	Confirmed screening laboratory values within the central laboratory ranges (haematology, renal and serum electrolyte parameters and	✓	✓	✓

Study Number: SMT C11005	Compound No.: SMT C1100
Protocol	Version: 5.0 24Feb2017

Criterion Number	Criterion	Cohort 1	Cohort 2	Cohort 3
	serum chemistry parameters) or considered not clinically significant in the opinion of the Investigator. Variations in specific parameters expected in a DMD population (e.g., AST, ALT, alkaline phosphatase, lactate dehydrogenase and CPK) classed by the Investigator as not clinically significant will not exclude the patient			
13	Be willing and able to comply with scheduled visits, drug administration plan, study procedures, laboratory tests and study restrictions	✓	✓	✓
14	Have taken part in a prior SMT C1100 study	NA	NA	✓

5.2.1.2. Exclusion Criteria

To be enrolled patients must not meet any of the selected criteria for their cohort:

Criterion Number	Criterion	Cohort 1	Cohort 2	Cohort 3
1	Have physical exam findings that in the investigator's opinion should be exclusionary e.g., lower limb injury that may affect 6MWD performance	✓	✓	✓
2	Have any change (initiation, change in type of drug, dose modification, schedule modification, interruption, discontinuation or reinitiation) in prophylaxis/treatment for congestive heart failure (CHF) within 3 months prior to the start of study treatment	✓	✓	✓
3	Have uncontrolled clinical symptoms and signs of CHF (American College of Cardiology/American Heart Association Stage C or Stage D)	✓	✓	✓
4	Have abnormal GLDH at baseline (>1.5 x ULN)	✓	✓	✓
5	Have abnormal coagulation times at baseline (>1.5 x ULN)		✓	✓
6	Have an abnormal ECG e.g., a QTcF >500 ms, left bundle-branch block or any other major conduction defect	✓	✓	✓
7	Use beta blockers (however, if during the course of the study they are clinically indicated they can be initiated)	✓	✓	NA
8	Use herbal supplements and be unwilling to stop these for the duration of the study	✓	✓	✓
8	Have a known hypersensitivity to any of the ingredients or excipients of the IMP. microfluidised oral suspension (F3): Poloxamer 188, Methylparaben, Propylparaben, Hydroxypropylmethyl cellulose, Glycerol, Non crystallising sorbitol [70%], Xanthan gum, Strawberry cream flavour [PHS-132963]	✓	NA	✓
10	Have a known hypersensitivity to any of the ingredients or excipients of the IMP. Powder for oral suspension (F6): hypromellose acetate succinate	NA	✓	NA
11	Have been exposed to another investigational drug or DMD interventional agent within 3 months prior to start of the Treatment Phase. Prior exposure to SMT C1100 or participation in an approved deflazacort access program (e.g., FOR-DMD or ACCESS DMD clinical trials) within this period would not exclude the patient (provided they have been on stable treatment for 6 months)	✓	✓	✓

Study Number: SMT C11005	Compound No.: SMT C1100
Protocol	Version: 5.0 24Feb2017

Criterion Number	Criterion	Cohort 1	Cohort 2	Cohort 3
12	Have a history of major surgical procedure within 12 weeks prior to the start of the Treatment Phase (Week 1)	✓	✓	✓
13	Be undertaking ongoing immunosuppressive therapy (other than corticosteroids)	✓	✓	✓
14	Have an expectation of a major surgical procedure (e.g., scoliosis surgery) during the 12-month Treatment Phase of the study	✓	✓	✓
15	Require daytime ventilator assistance	✓	✓	✓
16	Have a prior or ongoing medical condition (e.g., concomitant illness, psychiatric condition, behavioural disorder, alcoholism, drug abuse), medical history, ECG findings, or laboratory abnormality that, in the Investigator's opinion, could adversely affect the safety of the patient, makes it unlikely that the course of treatment or follow-up would be completed, or could impair the assessment of study results	✓	✓	✓
17	Be dairy or lactose intolerant or have any other dietary restrictions that might interfere with the conduct of the study	✓	✓	✓
18	Be a smoker, use other tobacco or nicotine products or be exposed to daily passive smoking (including parent/legal guardian, siblings) so as to minimise environmental factors causing CYP1A induction	✓	✓	✓
19	Be using an approved DMD medication or anticipates using one during the duration of the study e.g., ataluren, idebenone, drisapersen, Exondys51. Patients who are taking part in the FOR-DMD and ACCESS DMD studies will be allowed to take part	✓	✓	✓
20	Be using an inducer of CYP1A1 or CYP1A2	✓	✓	✓
21	Be using a substrate of CYP2B6	✓	✓	✓
22	All prescription, OTC, and herbal products that are known CYP2B6 sensitive substrates (e.g., bupropion, efavirenz) will be excluded 14 days prior to study conduct (beginning at screening) through 14 days after study conduct completion. Please note, this is not an exhaustive list of CYP2B6 substrates and a discussion with the Medical Monitor may be warranted	✓	✓	✓
23	Be using drugs that have serotonergic, norepinephrine or dopaminergic activity (e.g., selective serotonin reuptake inhibitors, serotonin norepinephrine reuptake inhibitors, tricyclic antidepressants, tryptophan, dextromethorphan, meperidine, bupropion, nortriptyline, desipramine, doxepin, amoxapine, rasagiline, selegiline), or treatments used in attention deficit hyperactivity disorder such as Methylphenidate, and phenethylamine (PEA)	✓	✓	✓
24	Use of substrates of BRCP (e.g., omeprazole, rabeprazole, fluvastatin, methotrexate, mitoxantrone, imatinib, irinotecan, lapatinib, rosuvastatin, sulfasalazine, topotecan)	✓	✓	✓

Study Number: SMT C11005 Protocol	Compound No.: SMT C1100 Version: 5.0 24Feb2017
---	---

6. STUDY ASSESSMENTS AND PROCEDURES

Each study patient in Cohorts 1 and 2 will require overnight hospitalisation at four time points during the study: Baseline, Week 24, Week 48 and End of study (Week 52). The purpose of these residential stays is to minimise patient activity immediately prior to certain biomarker assessments (i.e., CK) and physiological assessments (i.e., 6MWD, NSAA) as well as to facilitate pharmacokinetic sampling when conducted post-PM dose. Patients enrolled in Cohort 3 will not be required to attend residential stays.

Additional overnight hospitalisation may be requested to fit institutional requirements regarding biopsy or MRI procedures, however, this is not required.

6.1. Screening Procedures

6.1.1. Medical History

The patient's medical history will be collected by the Investigator, or suitably qualified designee. The information will be collected via an interview with the patient's parents or responsible adult and should include all diseases or conditions identified as relevant by the Investigator. The patient should be excluded from the trial if any disease or condition listed in the exclusion criteria is detected.

6.1.2. Demographics

The following demographic information should be recorded:

- Date of birth
- Sex
- Race
- Ethnicity (Hispanic/Latino or non-Hispanic/Latino)

Information that could identify the patient such as name, initials, social security number, (national) insurance number, etc. shall not be recorded in the CRF and should not be transmitted from the site to the Sponsor.

6.1.3. Nutritionist Appointment

The patient and their parents/responsible adult will meet with a nutritionist at the end of the screening process to discuss the nutritional requirements of the patient while they are enrolled in the study.

Study Number: SMT C11005	Compound No.: SMT C1100
Protocol	Version: 5.0 24Feb2017

6.2. Pharmacodynamic Procedures

6.2.1. Muscle Biopsy

Each patient in Cohorts 1 and 2 will undergo two muscle biopsies during the study at the times outlined in the Time and Events Table. Cohort 3 will not undergo muscle biopsies. The first eight patients in Cohort 1 will have a biopsy at 24 weeks and the remaining 22 patients will be alternately assigned between the 24 week and the 48 week time points. Six patients in Cohort 2 will undergo their second biopsy at 24 weeks and the remaining four patients at Week 48. The patient may have to travel and have the biopsy procedure undertaken at a different location to the patient's usual site of care. Ultrasound guidance is recommended though not required.

Patients who do not complete the 48-week dosing period may have their second biopsy at or around the Early Termination visit if it has not already been performed and they are willing to do so.

A detailed description of the methods relating to the collection of the biopsy sample and the processing of the sample can be found in the reference manuals. In order to detect whether daily dosing with SMT C1100 modulates the effect of utrophin with corresponding reduction in fibre regeneration within a muscle biopsy, the levels of utrophin protein at the myofibre membrane will be calculated for all fibres found in a biopsy section. In parallel, the quantity of regenerating fibres will also be calculated using markers of regeneration namely myosin protein intensity and myofibre cross sectional area.

Biopsy sampling may be performed using local or general anaesthetic according to the Investigator's clinical judgment as to which route is better for the patient. The biopsy should be taken from the biceps muscle.

6.2.2. Blood Biomarkers

Blood samples for analysis of biomarkers should be collected at the times outlined in the Time and Events Table.

Blood samples should be collected and details on collection and processing can be found in the laboratory manual. If patients have consented blood samples will be retained for future biomarker analysis.

Study Number: SMT C11005	Compound No.: SMT C1100
Protocol	Version: 5.0 24Feb2017

6.2.3. Magnetic Resonance Imaging

6.2.3.1. Leg Scan

Patients in Cohorts 1 and 2 will undergo MRI/MRS scans of the leg at the times outlined in the Time and Events Table.

The MRI scans will be performed using a 3 Tesla whole body instrument. The same machine should be used for all scans for an individual patient.

Further details on the MRI procedures can be found in the study reference manual. Patients should refrain from exercise for 24 h prior to each MRI procedure. Scans may be performed at a different location to the patient's usual site.

6.2.3.2. Cardiac Scan

Patients in Cohort 3 will undergo cardiac MRI scans at the times outlined in the Time and Events Table.

The MRI scans will be performed using a 3 Tesla whole body instrument. The same machine should be used for all scans for an individual patient.

Further details on the MRI procedures can be found in the study reference manual. Scans may be performed at a different location to the patient's usual site.

6.3. Pharmacokinetic Procedures

Blood samples for analysis of SMT C1100 parent and its metabolites (DHD I and DHD III) in plasma will be collected at the times outlined in the Time and Events Table. Day 7 (Cohort 2 only) and Week 4 and 8 assessments may be conducted by the sponsor-provided home nursing vendor

Pharmacokinetic samples for SMT C1100 and metabolites will be measured frequently. As this will be a sparse sampling pharmacokinetic assessment each patient in Cohort 1 and 2 will have three samples taken around either the AM dose or around the PM dose only. There will be six time points at which samples can be taken; pre-AM dose, 3 hours after the AM dose, 6 hours after the AM dose, or pre PM dose, 4 hours after the PM dose and 10 hours (+ up to 4 hours but before the next AM dose) after the PM dose. Sampling will be done around the AM dose during Day 1, Weeks 8, 12 and 36 (there is the option of samples being collected at the patient's house at the Week 8 time point). Sampling will be done around the PM dose during Weeks 4, 24 and 48 (there is the option of samples being collected at the patient's house at the Week 4 time point). Where the patient has been reduced to once-daily dosing only AM sampling points will be undertaken. For

Study Number: SMT C11005	Compound No.: SMT C1100
Protocol	Version: 5.0 24Feb2017

subjects in Cohort 2 a single additional sample will be taken at 4 h post-AM dose on Day 7.

In the Extension Phase all subjects, all cohorts will have a 4 h post-AM dose sample taken at the times outlined in the Time and Events Table.

For the 0–8 h samples a \pm 15 minute window will be allowed for each time point. Further details on collection, processing and shipping can be found in the laboratory and shipping manuals, respectively.

Samples for determination of SMT C1100 and metabolites (DHD I and DHD III and overall metabolite profile, as specified in the laboratory manual) concentrations in plasma will be analysed using appropriate bioanalytical methods, which will be described in a separate bioanalytical report.

6.4. Safety Procedures

6.4.1. Twelve-Lead Electrocardiogram

Twelve-lead ECGs will be performed at the times outlined in the Time and Events Table. A single ECG (in triplicate) will be performed at Screening, Baseline, Weeks 12 and 36. At Weeks 1, 24 and 48 ECGs will be performed pre-AM dose and 0.5, 2, 4 and 6 h post-AM dose or pre-PM dose and 0.5, 2 and 4 h post-PM dose.

TriPLICATE ECGs separated by approximately 2 to 5 minutes should be collected at each time point. The ECGs will be transmitted on an ongoing basis to a centrally based cardiologist who will independently examine the ECGs. Further details on performing and transmitting ECGs can be found in the Study Reference Manual.

Measurements will be made using an ECG machine that automatically calculates the heart rate and measures PR, RR, QRS, and QT.

All ECG traces will be reviewed and signed by the PI or a Study Physician and any abnormalities will be marked as clinically significant or not clinically significant. If the average QTc(F) is \geq 500 ms then an additional ECG should be repeated after at least a 5-minute interval.

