1.3.4. Risk Mitigation in Study SMT C11005

Three potential drug-related risks have been identified. One related to inhibition of the hERG channel by DHD I and DHD III, one related to potential interactions with concomitant medications, and one related to liver function test changes seen with F6.

The major metabolites of SMT C1100, DHD I and DHD III, caused between 25–45% inhibition of the hERG and human voltage-dependent calcium channel hCa_v1.2 at 30 µM. The highest individual plasma concentrations seen in patients dosed with F3 or F6 was at least 54-fold or 22-fold, respectively, below 30 µm for free DHD I and DHD III, and thus unlikely to cause QTc prolongation. However as a precaution and as this patient population is known to have significant ECG abnormalities and conduction defects, in this current and in previous clinical studies with patients with DMD, ECGs are being assessed frequently.

The preclinical pharmacokinetic studies indicated that SMT C1100 was primarily metabolized by CYP1A1 and CYP1A2. It was also shown that SMT C1100 could inhibit CYP1A1 and CYP1A2 in vitro; however, this inhibition was determined not to be clinically significant based on PBPK/Simcyp modelling (Study No. N-135). The metabolites of SMT C1100, DHD I and DHD III, were shown to induce CYP2B6. Based on the above, medication that induce CYP1A1 and/or CYP1A2 are restricted as are substrates of CYP2B6.

Study Number: SMT C11005	Compound No.: SMT C1100
Protocol	Version: 5.0 24Feb2017

SMT C1100, DHD I, and DHD III inhibited BCRP in vitro so given the role of this transporter in drug disposition and distribution, BCRP substrates are being excluded. DHD I and DHD III also inhibited OATP1B1 and OATP1B3 hepatic uptake transporters which could alter efficacy and increase the risk of exposure-dependent side effects of OATP1B1 and OATP1B3 substrates. Therefore, patients taking medications that are OATP1B1/1B3 substrates should be monitored for exaggerated pharmacological effects and exposure-dependent side effects as dose reduction may be needed. OATP1B1/1B3 substrates fluvastatin and rosuvastatin are also BCRP substrates and therefore excluded. Further details are provided in Section 9.2.

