8.3. Blinding

This is an open-label study so no blinding is required.

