5.4.4 Twelve-Lead Electrocardiogram (ECG)

Triplicate ECG measurements will be taken at screening, baseline, end of study, Day 1 and Weeks 12, 24, 36 and 48 during the first 48 weeks and then 6 monthly during the extension phase. If a subject withdraws from the study prematurely they will also be assessed at the termination visit.

Cohorts 1 and 2

On Day 1 and at Weeks 24 and 48 the measurements will be taken at either pre-AM dose and 0.5, 2, 4 and 6h post-AM dose OR pre-PM dose and 0.5, 2 and 4h post-PM dose. At Weeks 12 and 36 the measurements will be taken at 4h post-AM dose.

Cohort 3

At Weeks 12, 24, 36 and 48 the measurements will be taken at pre-AM dose and 0.5, 2, 4 and 6h post-AM dose.

Extension Phase

At Week 48 (start of extension phase) the measurements will be taken at 0.5, 2, 4 and 6h post-AM dose. Then measurements will be taken at 4h after dosing at each 6 monthly visit.

Heart rate, PR interval, RR interval, QRS complex and QT interval will be recorded. Heart rate corrected QTc will be determined using Fridericia (QTcF) and Bazett (QTcB) formulae.

The average of the triplicate measurements will be used in the summaries of data by visit, however individual replicates and unscheduled data will be used in categorical analyses (e.g. determining number

of subjects with a QTcF \geq 60ms). A categorical analysis will also be conducted based on the averages of the triplicate measurements.

Changes from baseline will be calculated for averaged triplicate data and for individual replicate data.

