9.8.5 Twelve-Lead Electrocardiogram

Observed values, baseline and changes from baseline will be summarized by visit for each ECG parameter.

The number (%) of subjects meeting the following criteria at any time after the start of dosing will also be tabulated:

Maximum PR interval

- < 170ms
- \geq 170ms

Also

- All values within 20% of change from baseline
- At least one value \geq 20% reduction from baseline, but no increases \geq 20% from baseline
- At least one value \geq 20% increase from baseline, but no reductions \geq 20% from baseline
- At least one value \geq 20% reduction from baseline and at least one value \geq 20% increase from baseline

Heart Rate

- All values within 20% of change from baseline
- At least one value \geq 20% reduction from baseline, but no increases \geq 20% from baseline
- At least one value \geq 20% increase from baseline, but no reductions \geq 20% from baseline
- At least one value \geq 20% reduction from baseline and at least one value \geq 20% increase from baseline

Maximum QTcF

- < 450ms
- \geq 450ms

Maximum increase from baseline in QTcF

- < 30ms
- 30ms - < 60ms
- \geq 60ms

This summary will present data for the first 24 weeks, first 48 weeks and the whole study.

The number (%) of subjects with ECG results in the following categories (per the investigator's interpretation) will be presented by visit/time point:

- normal
- abnormal - not clinically significant
- abnormal - clinically significant

The listing of ECG data will present the replicate data separately from the 'mean of replicate' data.

Values meeting the criteria of potential concern above will be flagged in listings.

Further analyses of QT, QTcF and Heart Rate, and PK:PD modelling investigating any relationship with exposure will be detailed in a separate QT analysis plan for the project and reported in a separate ECG report.

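### SAP 9.8.5 tabulates qualitative ECG findings only as by-visit counts of the open-label investigator's call, with no shift from baseline and no use of the central cardiologist's examination

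*Protocol*

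**What the plan says.** Protocol 6.4.1 sets up two looks at each ECG. One is central: "The ECGs will be transmitted on an ongoing basis to a centrally based cardiologist who will independently examine the ECGs". The other is local: "All ECG traces will be reviewed and signed by the PI or a Study Physician and any abnormalities will be marked as clinically significant", or as not clinically significant. On the intervals, the same section says: "Measurements will be made using an ECG machine that automatically calculates the heart rate and measures PR, RR, QRS, and QT". Protocol 8.3 adds: "This is an open-label study so no blinding is required".

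SAP 9.8.5 handles the two kinds of ECG data differently.

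- **Numeric parameters:** "Observed values, baseline and changes from baseline will be summarized by visit for each ECG parameter". There are also categories for maximum PR, 20% changes from baseline in PR and heart rate, maximum QTcF, and maximum QTcF increase. These are reported for the first 24 weeks, the first 48 weeks and the whole study. SAP 5.4.4 adds: "Changes from baseline will be calculated for averaged triplicate data and for individual replicate data".
- **Overall interpretation:** "The number (%) of subjects with ECG results in the following categories (per the investigator's interpretation) will be presented by visit/time point". The categories are normal, abnormal but not clinically significant, and abnormal and clinically significant. No shift from baseline is specified.

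Neither SAP 5.4.4 nor SAP 9.8.5 mentions the central cardiologist's examination.

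**The concern.** ECG is a secondary safety endpoint. Protocol 1.3.4 lists inhibition of the hERG channel first among three potential drug-related risks, and gives frequent ECGs as the precaution. Protocol 8.2, discussing the same channel effects, looks to the absence of arrhythmias and of ECG findings as reassurance. Qualitative findings are therefore part of the safety argument, alongside the QT interval.

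Protocol 1.3.4 also says that "this patient population is known to have significant ECG abnormalities and conduction defects". In such a population, with no control arm, the useful question is how many boys developed an abnormality that they did not have before dosing. Counts at each visit do not answer it. They also rest on readings at many sites by staff who know that the boy is on drug, although a single independent examiner has been arranged. At stake is whether a small number of new rhythm or conduction abnormalities would be visible in the planned tables.

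**Working it through.** The plan gives no figure to reproduce. The check sets the sections side by side and then asks what a by-visit count can show.

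**1. Which ECG findings have a within-boy summary in SAP 9.8.5?**

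- PR and heart rate: yes (change from baseline by visit, and 20% change categories).
- QTcF: yes (change by visit, and categories of maximum increase), plus a separate QT analysis plan.
- QRS: change from baseline by visit, but no threshold or change category. The separate plan names QT, QTcF and heart rate, not QRS.
- Rhythm, conduction pattern, morphology, overall normal or abnormal: no. The investigator table is the only tabulation.

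**2. Can boys enter with an abnormal ECG?** Exclusion criterion 6 (Protocol 5.2.1.2) gives QTcF above 500 ms, left bundle-branch block and other major conduction defects as its examples. Lesser abnormalities can remain, which fits the statement in Protocol 1.3.4.

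**3. What does a count at one time point show?** Let N be the boys assessed, A those abnormal at baseline, A_t those abnormal at time t, G the newly abnormal and R the resolved.

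A_t = A + G − R

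The table can show A and A_t but not G, which may lie anywhere from max(0, A_t − A) to min(A_t, N − A). Take N = 30 + 10 = 40, the planned size of Cohorts 1 and 2. The documents do not give A, so it is an assumption here:

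- A = 0: G = A_t exactly, so there is no ambiguity.
- A = A_t = 3: G lies between 0 and min(3, 37) = 3, that is, 0% to 3/40 = 7.5%.
- A = A_t = 20: G lies between 0 and 20, the widest case.

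In the second case, three new and three resolved abnormalities give the same row as no change at all.

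**4. What do the counts show across time points?** For a Cohort 1 or 2 boy on the morning series, the main phase has 5 (Day 1) + 1 (Week 12) + 5 (Week 24) + 1 (Week 36) + 5 (Week 48) = 17 scheduled time points. The Day 1 pre-dose ECG belongs to baseline, leaving 16. Suppose nobody is abnormal at baseline and the table shows one abnormal boy at each of the 16. The number of boys affected could be 1 (1/40 = 2.5%) or as many as 16 (16/40 = 40%). These are bounds, not expectations. They show that the number of boys ever newly abnormal cannot be recovered from the table even when A = 0.

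**5. Where do the intervals come from?** Protocol 6.4.1 describes machine measurement followed by central examination. The SAP does not say which values feed the PR and QTcF categories.

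**6. Is the missing layout foreign to this SAP?** No. It uses shift tables from baseline for orthoses, aids and falls (9.6.2), NSAA activities (9.6.3) and MRS fat fraction (9.7.1).

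**The case against.** The case on the other side is substantial.

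- **The named risk is handled elsewhere.** Protocol 1.3.4 frames hERG inhibition as a QTc question. QTcF has numeric within-boy categories and its own plan with exposure modelling. This stands, and it confines the point to qualitative findings.
- **Protocol and SAP do not conflict.** The protocol makes the site physician responsible for the clinical-significance call, and the SAP tabulates that call. Protocol 12.1.4.3 promises only changes from baseline in ECG parameters. This stands: the point is about a better summary, not a breach.
- **The central reading may not be usable.** The protocol says that the cardiologist examines the ECGs. It does not say that a category is recorded or that the reader is masked to visit. Every boy is on open-label drug, so a central reader knows that too. The Study Reference Manual and the QT plan might settle this, but they are not available here. This stands, so the central part of the fix is conditional.
- **New and old can be told apart by other routes.** Criterion 6 removes major defects, all data are listed by subject, and the definition of a treatment-emergent event separates new or worsened events. This stands only in part. Listings allow tracing by hand but are not a prespecified summary. An ECG finding reaches the adverse event tables only if the site reports it, so that route depends on the same judgement.
- **SAP 9.1 provides a baseline matched to the boys seen at each visit.** If that is applied to this table, it improves the comparison of totals but still gives only A and A_t.

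**Conclusion.** The point holds for qualitative ECG findings. Their only tabulation in SAP 9.8.5 is a net count of an open-label local reading, which cannot separate new from pre-existing abnormality or show how many boys were ever affected. It is a moderate reporting gap in a secondary safety endpoint and touches no MRI result.

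Its size depends on how many boys have an abnormal ECG at entry, which the documents do not give. If none do, the ambiguity at a single time point disappears, but the ambiguity across time points remains. The conclusion assumes that exclusion criterion 6 is applied in line with its examples, so that lesser abnormalities are admitted.

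A reader might infer two stronger things that the documents do not support:

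- **That drug-related ECG change in general is judged by the less objective of two readings.** It is not. PR, heart rate and QTcF change is assessed from measurements against each boy's own baseline.
- **That a blinded central category already sits in the database and would remove reader bias.** Independent does not mean masked, and storage of a central category is not stated. With no disagreement rate in the documents, no number of misclassified boys can be given.

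**What to change.** In SAP 9.8.5:

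1. Replace or supplement the by-visit table with a shift table of interpretation from the pre-dose baseline to the worst post-baseline result, for the first 24 weeks, the first 48 weeks and the whole study. These are the periods already used for the numeric categories. State how the triplicate readings at one time point reduce to a single category.
2. Where the central cardiologist's interpretation is recorded, tabulate it the same way beside the investigator's call and show the disagreements. If it is not recorded, say so.
3. State, here or in SAP 5.4.4, whether machine or centrally read intervals feed the PR and QTcF categories, and cross-refer to the QT analysis plan.

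Items 1 and 3 stand whether or not a central category exists.

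The cost is SAP wording, one or two extra tables and possibly a data transfer from the central reader. No new ECGs are needed. One caution applies: setting the worst of many post-baseline readings against one baseline category leans towards apparent worsening, and there is no control arm to calibrate it. Keeping the by-visit table alongside, and footnoting the number of post-baseline ECGs per boy, lets the reader allow for that.
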